8.3 Study Assessments

A summary of both baseline and follow up assessments is outlined in Table 1 (adults) and Table 2 (children) below. If appropriate consent is in place the subjects may undertake any combination of any of the investigations listed in the investigation table at any of these visits.

Table 1: Summary of adult assessments

		COPD		Asthma			Pn	eumo	nia	He	art Fail	Healthy		
Time point	1a	1b	2	1a	1b	2	1a	1b	2	1a	1b	2	1a	2
Written Informed Consent	Χ			Χ			Χ			Χ			Χ	
Collection of demographic data (age, gender, height, weight,	Χ^		Χ^	Χ^		Χ^	Χ^		Χ^	Χ^		Χ^	Χ	Χ
ethnicity, smoking status)*														
Time of date of admission/discharge#	Χ^	Χ^		Χ^	Χ^		Χ^	Χ^		Χ^	Χ^			
Breathless Scores*														
Patient defined breathlessness	Χ^		Χ	Χ^		Χ	Χ^		Х	Χ^		Χ	Χ	Χ
Extended MRC dyspnoea score	Χ^		Χ^	Χ		Χ	Χ		Χ	Χ		Χ	Χ	Χ
New York Heart Association Dyspnoea Score (NYHA)										Χ^		X^		
100 mm visual analogue breathlessness score	Χ		Χ	Χ		Χ	Χ		Χ	Χ		Χ	Χ	Χ
Exacerbation history (previous health care utilisation and	Χ^		Χ^	Χ^		Χ^	Χ^		Χ^	Χ^		Χ^	Χ	Χ
acute use of medication)*														
Quality of breath VOCs questionnaire	Х	Χ	Χ	Χ	Χ	Χ	Χ	Χ	Х	Х	Χ	Χ	Χ	Х
Structured Clinical History of presenting complaint and past	Χ^		Χ^	Χ^		Χ^	Χ^		Χ^	Χ^		X^	Χ	Х
medical history*														1
Assessment of acute disease severity#*		•								•				
DECAF Score	Χ^													
CURB 65 Score							Χ^							
BTS Asthma Severity Score				Χ^										
Heart failure risk calculator										Χ^				
Concurrent medication usage	Χ^	χ^	Χ^	Χ^	Χ^	Χ^	Χ^	Χ^	Χ^	Χ^	Χ^	X^	Х	Х
12 lead ECG*	Χ^			Χ^			Χ^			Χ^				
Chest X-ray*	Χ^		Χ^	Χ^		Χ^	Χ^		Χ^	Χ^		Χ^		
Health Status Questionnaires*														
Asthma Quality of Life questionnaire (AQLQ)				Χ		Χ^								
COPD assessment tool (CAT)	Χ		Χ^											

		COPD		1	Asthma	a	Pneumonia			Hea	art Fail	Healthy		
	1a	1b	2	1a	1b	2	1a	1b	2	1a	1b	2	1a	2
NASA Task Load Index	Χ		Χ	Χ		Χ	Χ		Χ	Χ		Χ	Χ	X
Blood tests*														
BNP	Χ^		Χ	Χ			Χ			Χ^		Χ^	Χ	
Troponin-I	Χ			Χ			Χ			Χ^			Χ	
CRP	Χ^		Χ^	X^		X^	X^		X^	Χ^		Χ^	Χ)
Full blood count + differential count	Χ^		Χ^	Χ^		X^	X^		X^	Χ^		X^	Χ)
DNA and RNA (PAXGENE)~	Χ		Χ	Χ		Χ	Χ		Χ	Χ		Χ	Χ	7
Plasma and serum	Χ		Χ	Χ		Χ	Χ		Χ	Χ		Χ	Χ	- 7
Arterial or capillary blood gas*#	Χ^			Χ^			X^			Χ^				
Peripheral blood flow cytometry	Χ		Χ	Χ		Χ	Χ		Χ	Χ		Χ	Χ	
Lung function test		•												
Spirometry*	Χ^		Χ^	Χ^		Χ^							Χ	- 2
Oscillometry*	Χ		Χ	Χ		Χ	Χ		Χ	Χ		Χ	Χ	2
Exhaled nitric oxide (FeNO)				Χ		X^								

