10. STATISTICS

participants.

10.1 Description of Statistical Methods (Detailed statistical anad analytical methods are outlined in the MRC-EMBER data analysis plan).

Primary Analysis

For the primary analysis the outcome is a nominal variable with levels (1) Acute breathlessness (2) Recovery form acute breathlessness. The relationship between the primary outcome and the metabolomics biomarkers in exhaled breath sample will be modelled using multinomial logistic regression. Acute

Page 32 of 46

breathlessness will be defined as one or more of (i) patient defined acute breathlessness and/or a (ii) 1 unit increase in Extended Medical Research Council breathlessness score (eMRC). In addition to metabolomics markers the following independent variables will be included in the model: age, sex, standard acute care pathology markers blood eosinophils, BNP, CRP, Troponin-I, canonical VOCs extracted from breath analysis and where relevant validated co morbidity scores (e.g. Charlson comorbidity score).

Adjudication

All acute/healthy adult patients' notes will be sequentially divided. These will then be reviewed and independently adjudicated by two independent respiratory consultants, blinded to admission bloods and diagnosis. The panel will independantly decide the primary diagnosis as well as mark their level of certainty on a 100 mm VAS scale. The panel member will then be able to review imaging, ECGs, and ABGs but not blood results. Results will be both -validated by separate panel member to ensure agreement using Bland-Altman and Correlations and within rater agreement will be assessed by replicate analysis of at least 20 cases 4 weeks apart.

Binary logistic regressions will be utilised to assess associations between VOCs and acute disease. ROC curves will be produced for individual predictors in the primary analysis. Additional techniques for multi variate analysis including but not limited to cluster analysis, structural equation modelling and topological data analyses will be applied where relevant. Tables of descriptive statistics will be compiled for all key variables. All analysis will be performed using SAS 9.4 http://www.r-project.org/.

Secondary Analysis

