10.2 The Number of Participants

The sample size for the study is based on the requirements of the multinomial logistic regression model for the primary analysis. We estimate that if the number of events to number of variables in the model is in the ratio 20:1 a sufficiently large sample size will be obtained [24]. We regard this study as being exploratory it will serve as a basis for determining the sample size required for a larger study in the future. (Appendix D)

- 10.3 The Level of Statistical Significance
- All tests will be performed at the 5% significance level.
- 10.4 Criteria for the Termination of the Trial. Last participant, last visit
 - 10.5 Procedure for Accounting for Missing, Unused, and Spurious Data. Describe

A table listing all key variables with percentage of missing data will be reported and where possible the reason for missing data will be reported. Missing data will be imputed using PROC MI in SAS. Spurious data will be reported and where possible correct values will be inserted, if it is not possible to supply correct values value will be deleted.

10.6 Procedures for Reporting any Deviation(s) from the Original Statistical Plan An interim sample size calculation will be performed at the end of the discovery phase (Quarter 2, year 3) of the project; this calculation will identify the optimal number of patients in each replication phase disease indicator group based upon the optimal number of metabolomic biomarkers associated with the disease and the key outcome data from the discovery phase e.g. risk prediction, 30 / 60 day re admissions, discrimination of disease state from healthy state.

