21.2 Closed formula for logistics regression models

82 acutely breathless adults (asthma:35, community acquired pneumonia :16, COPD:26) and 17 healthy controls were utilised for the analysis.

A panel of 10 pre specified aldehyde biomarkers derived from GCMS analysis were supplied. The biomarkers were normalised to a common standard and were not background subtracted.

A closed formula from Hsieh et al, Statis med 1998, was utilised to calculate sample sizes from logistic regression models of the 10 aldehydes with acute breathlessness as the outcome measure. The sample size estimates are also relevant to acute class comparions vs. the sum of other acute classes.

The results of the analyses are outlined in the figure below (each BRI number annotates a specific aldehyde).

Based upon the sample size estimates we would have an 80% power at the 5 % significance level to detect an odds ratio of association of 1.2 for a given disease class with 55 patients per disease class. Given the fact that MRC EMBER seeks to discover and replicate breath VOCs amongst 5 adults classes (CAP, heart failure, COPD, asthma and healthy aged matched subjects).

We would require 110 patients per class – 550 patients across the program to achieve these aims.

Commented [CSB1]: This is not a complete sentence. There is a clause missing, or else the punctuation needs adjustment.

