21.3 Closed formula for sensitivity and specificity of disease biomarkers

Page 44 of 46

The closed formulae in Tilaki-Hajjan *et al*, Journal of Biomedical Informatics 48(2014), 193-2014, were also utilised to understand the power that the samples size above would provide with respect to biomarker sensitivity and specificity.

The following assumptions were made:

- That a sensitivity of 80 % with a precision (d) of between 5-8% would provide a useful biomarker capable of 'ruling out' an acute class. The same target was applied to specificity.
- We assume a prevalence of acute breathlessness of 80% as the MRC EMBER campaign
 uses acute breathlessness as the initial stratification tool for recruitment and 1:5 patients
 recruited will be non-breathless healthy controls. We aim to balance group sizes across
 classes equally.
- A type 1 error rate of 0.05 and power of 95% CI level, 90% CI level
- Note for a prevalence ≥ 50% Nspec ≥ Nsens is always the case, so N_{spec} is the number we need to consider.

95% CI, precision ± 5%

 N_{sens} = 1.96² x 0.8 x 0.2 / 0.05² x 0.8 = 307

 N_{spec} = 1.96² x 0.8 x 0.2 / 0.05² x 0.2 = 1,230

90% CI, precision ± 5%

 N_{sens} = 1.64² x 0.8 x 0.2 / 0.05² x 0.8 = 215

 N_{spec} = 1.64² x 0.8 x 0.2 / 0.05² x 0.2 = 861

To obtain n near 550, increase the maximum marginal error d (i.e. decrease the precision)

95% CI, precision ± 8%, Prevalence = 80%, Sensitivity and Specificity=80 %

 $N_{sens} = 120$

 $N_{\text{spec}} = 480$

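### The primary contrast in section 10.1 is acute versus recovery, but Appendix C sizes other contrasts, and two model covariates are not scheduled at the recovery visit in all adult groups

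*Protocol*

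**What the plan says.** Section 10.1 gives the primary outcome two levels: "For the primary analysis the outcome is a nominal variable with levels (1) Acute breathlessness (2) Recovery form acute breathlessness". Section 6.1 defines recovery as patient-reported or clinician-defined, at least 6 weeks after the event, and assesses it at visit 2. Both levels therefore come from the same patients. The independent variables in 10.1 include "age, sex, standard acute care pathology markers blood eosinophils, BNP, CRP, Troponin-I".

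Section 10.2 ties the numbers to this model: "The sample size for the study is based on the requirements of the multinomial logistic regression model for the primary analysis". It gives a rule of 20 events per variable and calls the study exploratory.

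Appendix C holds the calculation:

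- Section 21.2 reports that 82 acute adults "and 17 healthy controls were utilised for the analysis". It adds that the estimates also serve comparisons of one acute class with the rest.
- Section 21.3 assumes 80% prevalence of acute breathlessness, because one in five patients "recruited will be non-breathless healthy controls". After finding 1,230 for specificity at ±5%, it continues: "To obtain n near 550, increase the maximum marginal error d (i.e. decrease the precision".
- Section 21.4 concludes that 550 people (five classes of 110, healthy being one) support 80% ± 8% for discovery, and that replication is powered for sensitivity but not for specificity.

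Section 5.1 lists healthy controls under the primary objective, which also asks for PPV and NPV. In section 8.3, "Table 1: Summary of adult assessments" sets out which tests are planned at 1a, 1b and 2.

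**The concern.** The people who count as non-cases differ between the two places. In 10.1 they are the acute patients after recovery. In Appendix C they are separate healthy volunteers, or patients in other acute classes. Specificity rests on the number of non-cases, and PPV and NPV rest on the ratio of cases to non-cases. The choice therefore changes three of the four measures in the primary objective. Someone who takes 10.2 at its word will apply the ±8%, and the warning about replication, to an analysis that neither describes.

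The covariates raise a linked question. Section 10.1 says BNP and Troponin-I will be in the model, but Table 1 does not plan either at recovery for all adult groups. If the model needs a value at each visit, that value is not planned for one level of the outcome.

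**Working it through.** **Inputs.** Sensitivity and specificity 80%, prevalence 80%, precision 5% or 8% (21.3). Four adult acute classes of 55 per phase, so 220, and 55 healthy adults per phase (21.5). Planned range for healthy adults: 55–150 in discovery, 55–75 in replication (7.1). The protocol gives no visit 2 loss. The 14% used below is the 3-month COPD mortality in 9.1.5; 30% and 50% are assumptions. Each patient is taken to give one acute record and at most one recovery record. All figures are for adults.

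**1. The plan's own figures.** N_sens = z²·p(1−p)/(d²·prev) and N_spec = z²·p(1−p)/(d²·(1−prev)), with p = 0.8 and prev = 0.8.

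| Setting | Computed N_sens / N_spec | Printed |
|---|---|---|
| 95%, ±5% (z = 1.96) | 307.3 / 1,229.3 | 307 / 1,230 |
| 90%, ±5% (z = 1.64) | 215.2 / 860.7 | 215 / 861 |
| 95%, ±8% (z = 1.96) | 120.0 / 480.2 | 120 / 480 |

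All six agree within rounding, and they hold for 80% acute and 20% healthy.

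**2. Non-acute records needed.** For ±8%: 1.96² × 0.16 / 0.08² = 96.04, so 97. For ±5%: 1.96² × 0.16 / 0.05² = 245.9, so 246.

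**3. Specificity under each contrast.** Half-width = 1.96·√(0.16/n).

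| Non-cases | n | 95% half-width |
|---|---|---|
| Healthy, one phase, minimum | 55 | ±10.6% |
| Healthy, replication, maximum | 75 | ±9.1% |
| Healthy, discovery, maximum | 150 | ±6.4% |
| Healthy, both phases, minimum | 110 | ±7.5% |
| Recovery, one phase, no loss | 220 | ±5.3% |
| Recovery, one phase, 14% loss | 189 | ±5.7% |
| Recovery, one phase, 30% loss | 154 | ±6.3% |
| Recovery, one phase, 50% loss | 110 | ±7.5% |
| Recovery, both phases, no loss | 440 | ±3.7% |

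With healthy controls, replication cannot reach ±8%, because its maximum of 75 is below 97. With recovery records, each phase stays within ±8% while at least 97 of 220 (44%) give one. The ±5% that Appendix C gave up needs 246 of the combined 440 (56%). Sensitivity is ±5.3% per phase (220 acute records) under either contrast.

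**4. Predictive values at 80% sensitivity and specificity.** PPV = 0.8p/(0.8p + 0.2(1−p)); NPV = 0.8(1−p)/(0.8(1−p) + 0.2p), where p is the acute share.

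- p = 0.8: PPV = 0.64/0.68 = 94%; NPV = 0.16/0.32 = 50%.
- p = 0.5 (one acute and one recovery record each): PPV = NPV = 0.40/0.50 = 80%.

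**5. Covariates at visit 2 in Table 1.**

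| Covariate | COPD | Asthma | Pneumonia | Heart failure |
|---|---|---|---|---|
| Troponin-I | no | no | no | no |
| BNP | yes | no | no | yes |
| CRP | yes | yes | yes | yes |
| Blood count with differential (eosinophils) | yes | yes | yes | yes |

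Per phase, Troponin-I is unscheduled for all 220 possible recovery records and BNP for 55 + 55 = 110 of them. Healthy adults have both tests at 1a. Table 2 has no row for either test, so children lack both under either contrast.

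**The case against.** Five points can be made for the plan.

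- **Section 10.2 has its own rule, 20 events per variable, and calls the study exploratory.** The rule does belong to the primary model. But it gives no precision for sensitivity or specificity, 10.2 counts no variables, and Appendix C does not use it. The conclusions in 21.4 remain statements about precision and power.
- **Appendix C says openly who its non-cases are.** This stands. A reader of 21.3 can see that the figures are for acute versus healthy. What is missing is any figure for acute versus recovery.
- **Section 10.6 does not define a second primary contrast.** It mentions "discrimination of disease state from healthy state", but within a list of examples that also includes readmission. This stands, and the point does not rest on 10.6.
- **Admission values may be intended.** Section 10.1 describes BNP, Troponin-I and the others as acute care markers and does not say they must be measured again at recovery. Admission values used as patient-level covariates would fill both records. Section 8.3 also permits any listed test at any visit. So the covariate problem depends on visit-specific values being meant. If they are, no recovery Troponin-I values are planned for a complete-case analysis, or for the PROC MI imputation in 10.5 to draw on.
- **The 1:1 split is a simplification.** Breath is sampled at both 1a and 1b, readmitted patients may be assessed again, and attending visit 2 is not the same as meeting the recovery definition. This stands, and it is why the recovery figures are stated as conditional.

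How the model treats two records from one patient may be set in the data analysis plan that 10.1 cites. It is not part of this point.

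**Conclusion.** The sizing in Appendix C does not describe the analysis that 10.1 calls primary, although 10.2 says the sample size is based on that analysis. The statement in 21.4 on specificity in replication holds for acute versus healthy (±9.1% to ±10.6%). It does not hold for acute versus recovery while at least 97 of 220 adults per phase give a recovery record. These figures assume Wald intervals, one acute record per patient and the minimum adult numbers, with visit 2 loss as a range because the protocol gives none.

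Three stronger readings are tempting and are not supported:

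- *The primary analysis is too small.* The reverse is nearer the truth: precision for acute versus recovery is better than Appendix C states.
- *The 10.1 covariates are not measured at recovery.* CRP, eosinophils, age and sex are available. The gap is Troponin-I in all adult groups and BNP in asthma and pneumonia.
- *No single primary contrast is stated.* Section 10.1 states one; the other sections do not follow it.

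The point should be acted on, but it is a matter of reconciling text rather than a flaw in the data to be collected.

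**What to change.** Make 10.1, 10.2 and Appendix C describe one primary contrast. The sponsor can choose either route.

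- **Keep acute versus recovery.** Replace the precision figures in 21.3 and the specificity statement in 21.4 with figures for this contrast, per phase and combined, over a stated range of visit 2 loss. In 10.1, either remove Troponin-I, and BNP where it is unscheduled, as visit-specific covariates, or state that admission values enter as patient-level covariates. The cost of removal is less adjustment in the primary model.
- **Change to acute versus healthy.** Make healthy a level of the 10.1 outcome and state specificity precision per phase: ±10.6% to ±6.4% in discovery and ±10.6% to ±9.1% in replication, over the planned ranges. The cost is that a less favourable figure must be printed than the ±8% now given.

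Under either route, state the acute share behind any PPV or NPV, and say what the model does for children, for whom neither BNP nor Troponin-I is scheduled. The work is wording and minor programming, with no new data.

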Sputum sample (spontaneous^ or induced)	Χ^		Χ	X^		Χ	X^		Χ	X^		Χ	Χ	
Volatile organic compounds (VOCs)	Χ	Χ	Χ	Х	Χ	Χ	Χ	Χ	Χ	Х	Χ	Χ	Χ	
Urine sample*	Χ		Χ	Χ		Χ	Χ		Χ	Χ		Χ	Χ	
Echocardiography*	Х									Χ^				
Quadriceps ultrasound	Х	Х	Х											
4 meter gait speed		Χ	Χ								Χ	Χ		
Review of Adverse Events & Serious Adverse Events		Χ	Χ		Χ	Х		Χ	Χ		Χ	Χ		7
Physical Exam*	χ^		Χ^	χ^		Χ^	Χ^		Χ^	χ^		Χ^	Х	

^{*}Can be performed at time points 1a or 1b. for healthy volunteers this can be completed at visit 1 or 2. For informed consent see protocol, ^ may be part of routine clinical care according to UHL Trust Guidelines. Arterial, capillary blood gases and blood cultures only done in selected clinical cases, # Acute patients only ~If DNA taken at time point 1a will not be repeated at timepoint 2.

Table 2: Summary of children assessments

essments		hood WI firmed A	Hea	thy	
Time point	1a	1b	2	1a	2
Written Informed Consent	Х			Х	
Collection of demographic data (age, gender, height, weight, ethnicity, smoking status)*	Χ^		Χ^	Х	Х
Time of date of admission/discharge#	Χ^	X^			
100 mm visual analogue breathlessness score*	Х		Х	Х	Х
Exacerbation history (previous health care utilisation and acute use of medication)*	Χ^		Χ^	Х	Х
Quality of breath VOCs questionnaire	Χ	Х	Χ	Х	Х
Structured Clinical History of presenting complaint and past medical history*	Χ^		Χ^	Х	Х
Concurrent medication usage	Χ^	Χ^	Χ^	Х	Х
Chest X-ray*	Χ^		Χ^		
Health Status Questionnaires*					
Asthma control questionnaire (ACQ)	Χ^		Χ^		
Asthma quality of life questionnaire (AQLQ)	Χ^		Χ^		
NASA Task Load Index	Х	Х	Х	Х	Х
Blood tests*+\$					
CRP	Χ^		Χ^	Х	Х
Full blood count + differential count	Χ^		Χ^	Х	Х
DNA and RNA (PAXGENE)	Х		Х	Х	Х
Plasma and serum	Х		Х	Х	Х
Arterial or capillary blood gas*	Χ^				
Blood culture*	Χ^				
Lung function test					
Spirometry*	Χ^		Χ^	Х	Х
Exhaled nitric oxide (FeNO)	Х		Х	Х	Х
Sputum sample (spontaneous^ or induced)\$	Χ^		Χ^	Х	Х
Volatile organic compounds (VOCs)	Х	Х	Х	Х	Х
Urine sample*	Х		Х	Х	Х
Review of Adverse Events & Serious Adverse Events		Х	Х		Х
Physical Exam*	Χ^		Χ^	Х	Х

^{*}Can be performed at time points 1a or 1b. For informed consent see protocol, ^ Part of routine clinical care as part of the University Hospitals of Leicester, acute care clinical pathway. Will be performed in selected clinical cases based on clinical need, # Acute patients only, + up to 35 mls maximum per visit, ⁵ optional

A description of the research assessments is outlined below

Demographics

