In addition to the routine clinical blood samples will be taken for RNA and DNA, serum and plasma, peripheral blood cell flow cytometry analysis per visit. This may total up to 85 mls for an adult and 35mls for a child. Samples will be barcoded and stored at the investigative site in dedicated -80 C freezers. Samples may be transferred to the NIHR national bio sample centre subject to available funding. Blood samples will be taken at the same time point as the clinical samples to minimise inconvenience to the patient.

• Health Questionnaires

Questionnaires regarding the subjects' health and disease status will be completed. These will include measures of health status.

NASA Task Load Index

It is a widely used, subjective, multidimensional assessment tool that rates perceived workload in order to assess a task, system, or team's effectiveness or other aspects of performance. It assesses work load on five 7-point scales including mental demand, physical demand, temporal demand, performance, effort and Page 29 of 46

frustration. Increments of high, medium and low estimates for each point result in 21 gradations on the scales. This tool will be incorporated into EMBER to assess the overall performance and feasibility of using ReCIVA mask in breath collection.

• Physical performance

4 meter gait speed (the time it takes to walk 4 meters) and quadriceps size measured using ultrasound will be performed to assess physical performance in selected patients. Both are measures of frailty, non-invasive, and validated in the acute care setting in chronic respiratory disease. If ultrasound measure is missed at timepoint 1 then it will not be taken at timepoint 2.

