21.5 Recruitment Plan: Acute Adult Study

Disease Category	Discovery	Replication
Acute Adult Asthma	55	55
Acute COPD	55	55
Acute Heart Failure	55	55
Community Acquired	55	55
Pneumonia		
Adult healthy volunteers	55	55

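### The primary acute-versus-recovery model is to include Troponin-I and BNP, but Table 1 schedules no Troponin-I at visit 2 in any adult disease group and BNP in only two of four

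*Protocol*

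**What the plan says.** Section 10.1 defines the primary outcome thus: "the outcome is a nominal variable with levels (1) Acute breathlessness (2) Recovery form acute breathlessness". For the multinomial logistic model it states that "the following independent variables will be included in the model: age, sex, standard acute care pathology markers blood eosinophils, BNP, CRP, Troponin-I", followed by breath VOCs and comorbidity scores. Only the comorbidity scores carry a where-relevant condition; the four blood markers carry none.

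The recovery level comes from visit 2, at least 6 weeks and up to 6 months after the event (synopsis and Section 6.1).

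Table 1 in Section 8.3 fixes which blood tests are scheduled at which visit. Three other provisions bear on the point:

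- The Table 1 footnote for starred items, which include the blood tests: "Can be performed at time points 1a or 1b. for healthy volunteers this can be completed at visit 1 or 2".
- The introduction to the assessments, subject to consent: "the subjects may undertake any combination of any of the investigations listed in the investigation table at any of these visits".
- Section 10.5: "Missing data will be imputed using PROC MI in SAS".

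**The concern.** A covariate in a model that contrasts two states has to be observed in both states if the model is to adjust for its difference between them. Here the covariate list and the visit schedule are both fixed in the protocol, and they do not fit together. 10.1 also does not say whether the blood markers enter visit by visit or as a single admission value, and neither reading works for Troponin-I.

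At stake is how the primary estimate is read. A breath-marker odds ratio described as adjusted for Troponin-I and BNP invites the conclusion that breath adds information beyond those tests. For Troponin-I the planned data cannot support that conclusion.

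**Working it through.** **Step 1: the schedule.** Each blood-test row of Table 1 has 14 cells: three visits for each of four disease groups and two for healthy volunteers. The marks at visit 2 are:

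| Marker | COPD | Asthma | Pneumonia | Heart failure |
|---|---|---|---|---|
| Troponin-I | no | no | no | no |
| BNP | yes | no | no | yes |
| CRP | yes | yes | yes | yes |
| Full blood count with differential | yes | yes | yes | yes |

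All four markers are scheduled at 1a in all four groups. The neighbouring CRP and blood count rows carry full visit 2 marks, so the blanks are not a sign of a broken table.

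**Step 2: counts.** Section 21.5 plans 55 adults per disease class per phase. Assuming full attendance, there are 4 × 55 = 220 adult recovery records per phase and 440 over both.

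| Marker | Scheduled at recovery, per phase | Both phases |
|---|---|---|
| Troponin-I | 0 of 220 | 0 of 440 |
| BNP | 55 + 55 = 110 of 220 | 220 of 440 |
| CRP | 220 of 220 | 440 of 440 |
| Eosinophils | 220 of 220 | 440 of 440 |
| All four | 0 of 220 | 0 of 440 |

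At 1a all four are scheduled in 220 of 220 per phase. Children are left out of the count because Table 2 schedules neither patient-defined breathlessness nor eMRC.

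**Step 3: can another provision fill the gap?**

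- The footnote moves patients' tests between 1a and 1b. Its visit 1 or 2 option is for healthy volunteers.
- The any-visit clause permits a test but schedules none.
- With complete cases on scheduled data, no recovery records remain and the model cannot be fitted.
- PROC MI would return values. With no recovery Troponin-I scheduled, the acute-recovery difference would come from the imputation model and not from data. Recovery BNP in asthma and pneumonia would be borrowed from COPD and heart failure.
- If the 1a value is used in both states, each patient has the same value at both outcome levels. Adding a constant t to every acute Troponin-I value then changes only the intercept, so the breath-marker estimate cannot respond to the size of the true shift.

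**Step 4: possible size (illustration; every input is assumed).** Take a breath marker, CRP, eosinophils and Troponin-I in SD units, with common pairwise correlation ρ and acute shifts of 0.5, 1, 0 and t. The log odds ratios are the inverse covariance matrix times the shift vector. For the breath marker:

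- with Troponin-I truly adjusted: [0.5 − ρ(1.5 + t)/(1 + 3ρ)]/(1 − ρ)
- with Troponin-I left out: [0.5 − 1.5ρ/(1 + 2ρ)]/(1 − ρ)

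At ρ = 0.3 and t = 2, the adjusted value is [0.5 − 0.3 × 3.5/1.9]/0.7 = −0.08. Left out, it is [0.5 − 0.45/1.6]/0.7 = 0.31.

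| ρ | Adjusted, t = 0 | t = 0.5 | t = 1 | t = 2 | Left out |
|---|---|---|---|---|---|
| 0 | 0.50 | 0.50 | 0.50 | 0.50 | 0.50 |
| 0.1 | 0.43 | 0.38 | 0.34 | 0.26 | 0.42 |
| 0.3 | 0.38 | 0.26 | 0.15 | −0.08 | 0.31 |
| 0.5 | 0.40 | 0.20 | 0.00 | −0.40 | 0.25 |

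A paired simulation (220 patients, within-patient correlation 0.5, 60 repeats, 5 imputations drawn from the acute rows) gave a mean imputed Troponin-I coefficient between −0.02 and 0.01 in all 16 settings. The imputed and left-out breath-marker values differed by at most 0.01. Under that imputation model, imputing Troponin-I amounts to leaving it out.

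**The case against.** The strongest reply has four parts.

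- **Covariate timing may sit in the data analysis plan.** The heading of 10.1 points to that plan, which is not at hand. Calling the tests acute care markers fits an admission value, and on that reading nothing is missing by design. That is a fair reading, but 10.1 does not state it, and an admission value cannot adjust for change between the two states. Nor can an analysis plan create visit 2 values that the protocol does not schedule.
- **Unscheduled does not mean unavailable.** Extra tests are permitted and hospital results feed the database, so the counts describe the schedule and do not predict the data. This stands as a limit on the counts. Troponin-I taken at visit 2 only in selected patients would still not supply the recovery level properly.
- **10.5 also promises a table of percentage missing for key variables.** That would alert a careful reader: Troponin-I would be missing in 220 of 440 acute-plus-recovery rows per phase. It weakens the argument that the gap stays hidden, but it does not make the effect estimable.
- **The illustration has no inputs from the protocol.** That is correct. With zero correlation there is no harm. With correlation 0.1 between breath marker and Troponin-I only, the adjusted value runs from 0.5/0.99 = 0.51 at t = 0 to 0.3/0.99 = 0.30 at t = 2, against 0.50 left out, with no change of sign. The agreement between imputed and left-out values rests on the imputation model assumed. Non-identification itself does not depend on the illustration.

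**Conclusion.** The concern holds. As written, the primary model names a covariate, Troponin-I, with no scheduled value at one of its two outcome levels (0 of 220 adult recovery records per phase), and another, BNP, scheduled at that level in half of them (110 of 220). The counts rest on Table 1, the minimum of 55 per class and full attendance. The size of any distortion in the breath-marker estimate is unknown: nil if the markers are uncorrelated, and possibly large, in either direction, if they are correlated.

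The reach is limited. ROC curves for individual breath markers are unaffected, CRP and eosinophils are adequately scheduled, and Section 10.2 calls the study exploratory. It should nevertheless be corrected, because it concerns the stated primary model and what can be claimed from it.

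**What to change.** 1. In 10.1, limit the visit-matched pathology covariates of the primary model to those scheduled at both 1a and 2 in all four adult disease groups: CRP and blood eosinophils.
2. In 10.5, state that a marker not scheduled at an outcome level is not imputed for that level.
3. Do not describe the primary estimates as adjusted for Troponin-I or BNP. A BNP-adjusted sensitivity analysis in COPD and heart failure alone remains possible, with 110 of 110 recovery records scheduled per phase.

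This costs wording in 10.1, 10.5 and the data analysis plan. What is given up is the adjusted label for two markers.

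If adjustment for both markers is wanted, Table 1 and 10.1 must be reconciled. Alternatively, Table 1 schedules "Plasma and serum" at visit 2 in all four groups, and of the blood samples the protocol says: "Samples will be barcoded and stored at the investigative site in dedicated -80 C freezers". Those could be assayed if suitable, which the protocol does not address. Either route means up to 220 Troponin-I and 110 BNP visit 2 assays in adults per phase at the minimum sample size.
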